#### *Nephrotoxicity*

Cisplatin causes severe cumulative nephrotoxicity. A urine output of 100 mL/hour or greater will tend to minimize cisplatin nephrotoxicity. This can be accomplished by prehydration with 2 liters of an appropriate IV solution, and similar post cisplatin hydration (recommended 2,500 mL/m^2/24 hours) or according to institutional standards. If vigorous hydration is insufficient to maintain adequate urinary output, an osmotic diuretic may be administered (eg, mannitol).

#### *Neuropathies*

Neuropathies may manifest by paresthesia, areflexia, and a proprioceptive loss of sensation of vibrations. A neurologic examination must be carried out at regular intervals.

#### *Ototoxicity*

Ototoxicity has been observed in up to 31% of patients treated with a single dose of cisplatin 50 mg/m^2, and is manifested by tinnitus and/or hearing loss in the high frequency range (4000 to 8000 Hz).

*Allergic phenomena*

As with other platinum-based products, hypersensitivity reactions appearing in most cases during perfusion may occur, and necessitate discontinuation of the perfusion as an appropriate symptomatic treatment.

Anaphylactic-like reactions to cisplatin have been observed. These reactions can be controlled by administration of antihistamines, adrenaline, and/or glucocorticoids.

*Hepatic function and hematological status*

The hematological status and the hepatic function must be monitored at regular intervals.

*Injection site reactions*

Injection site reactions may occur during the administration of cisplatin. Given the possibility of extravasation, it is recommended to closely monitor the infusion site for possible infiltration during drug administration.

Special care is required for subjects with acute bacterial or viral infections.

Table 5.5 lists toxicities and related dose modifications and discontinuations.

**Table 5.5: Cisplatin Dose Modifications and Discontinuations\* for Toxicities**

Toxicity	Dose Modification/Discontinuation
Hematological	A repeat course should not be given until circulating blood elements are at an acceptable level (ie, platelets $\geq 100 \times 10^9/L$ , white blood cells $\geq 4 \times 10^9/L$ )
Febrile neutropenia/infection	The first episode of febrile neutropenia or infection will result in reduction by 20% of cisplatin dose. If there is a second episode, despite dose reduction, the subject must receive prophylactic antibiotics during subsequent cycles. If there is a third episode, the subject will be withdrawn from study.
Neutropenia	Grade 2 or 3: cisplatin treatment delay until < Grade 1. Grade 4: cisplatin treatment delay until < Grade 1; dose reduction of all further doses of cisplatin by 20%.
Nephrotoxicity	A repeat course of cisplatin should not be given until the serum creatinine is below 1.5 mg/100 mL, and/or the urea is below 25 mg/100 mL
Thrombocytopenia	Grade 1: cisplatin treatment delay until platelets $\geq 100,000/mm^3$ . $\geq$ Grade 2: cisplatin treatment delay until platelets $>100,000/mm^3$ , dose reduction of all further doses of cisplatin by 20%

Toxicity	Dose Modification/Discontinuation
Organ Toxicity	Grade 2: Delay chemotherapy until $\leq$ Grade 1. $\geq$ Grade 3 or more: Delay chemotherapy until $\leq$ Grade 1; dose reduction of all further doses of cisplatin by 20%. Do not delay or reduce cisplatin dose if there are asymptomatic increases in transaminases, cetuximab-induced skin reactions, and subclinical side effects (e.g. nausea, vomiting, alopecia, altered taste).
Ototoxicity	Criteria for hearing testing
Neuropathy	In case of sensory neuropathy $\geq$ Grade 2, change cisplatin to carboplatin

Note: Please refer to the cisplatin package insert for additional information on potential toxicities and their management. When cisplatin is administered in combination with other agents such as cetuximab, refer to their respective product information. \*If events do not recover within 3 weeks, discontinue cisplatin treatment.

#### 5.1.7.4. Dose Modification of Carboplatin

##### *Myelosuppression*

Carboplatin myelosuppression is closely related to its renal clearance. Subjects with abnormal kidney function or receiving concomitant therapy with other drugs with nephrotoxic potential are likely to experience severe and prolonged myelotoxicity. Renal function parameters should therefore be carefully assessed.

##### *Hematological toxicity*

Leukopenia, neutropenia, and thrombocytopenia are dose-dependent and dose-limiting. Anemia is frequent and cumulative. Frequent monitoring of peripheral blood counts is recommended during and following therapy. Carboplatin should not be repeated until after leukocytes, platelets, and neutrophils have returned to normal ([Table 5.6](#)).

##### *Hepatic and/or renal insufficiency*

Renal or hepatic function impairment may be encountered with carboplatin. Dose reduction or discontinuation of carboplatin is required in the presence of moderate to severe alterations in renal or hepatic function.

##### *Allergic reactions*

Infrequent allergic reactions such as erythematous rash, fever with no apparent cause, or pruritus, anaphylaxis, angioedema, and anaphylactoid reactions (including bronchospasm, urticarial, and facial oedema) may occur. These occur more often during perfusion. Discontinuation of the perfusion should be carried out immediately and appropriate symptomatic treatment must be given such as with antihistamines, adrenalines, and/or glucocorticoids.

##### *Neurotoxicity*

Neurotoxicity such as paresthesia, decreased deep tendon reflexes, and ototoxicity are more likely in subjects older than 65 years old. Monitoring and neurological examinations should be carried out at regular intervals.

**Table 5.6: Carboplatin Dose Modification for Toxicities**

Toxicity	Dose Reduction a		
Myelosuppression*	Platelets	Neutrophils	Adjusted Dose (from prior course)
	> 100,000	> 1,500	No adjustment
	50-100,000	500-1,500	No Adjustment
	< 50,000	< 500	25% dose reduction
Nephrotoxicity*	Baseline creatinine clearance		Recommended Dose on Day 1
	41-59 mL/min		AUC 3.75 (25% dose reduction)
	30-40 mL/min		AUC 3.0 (40% dose reduction)

a Initial dose is AUC 5 calculated by Calvert formula. AUC = area under the curve.

Note: Please refer to the carboplatin package insert for additional information on potential toxicities and their management. When carboplatin is administered in combination with other agents such as cetuximab, refer to their respective product information.

\*If events do not recover within 3 weeks, discontinue carboplatin treatment.

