  25. Receiving yellow fever vaccine or live attenuated vaccines (for subjects receiving carboplatin)
  26. Presence of hemorrhagic tumors (for subjects receiving carboplatin)
  27. Prophylactic use of phenytoin or fosphenytoin (for subjects receiving cisplatin or carboplatin)
- 

Dosage Form, Dose and  
Route of Administration:

Patritumab

Placebo lyophilisate will be diluted in an identical manner in 8 mL water.

The order of IV administration will be:

1. Patritumab or placebo
  - Patritumab/placebo initial loading dose [REDACTED] over 60 minutes ( $\pm$  10 minutes) followed in cycle 2 and beyond with a maintenance dose of [REDACTED] over 60 minutes ( $\pm$  10 minutes) every three weeks
    - Infusion time can be extended to a maximum of 120 minutes for subjects unable to tolerate the 60 minute infusion
2. Cetuximab
  - Cetuximab initial dose at 400 mg/m^2 IV as a 2-hour infusion on Week 1, followed by 250 mg/m^2 over 60 minutes weekly, plus

One hour after the end of the cetuximab administration infuse with either:

3. Cisplatin OR carboplatin selected at the discretion of the Investigator.
    - Cisplatin at 100 mg/m^2 IV infused over 1 hour, every three weeks up to a maximum of 6 cycles
      - Pretreatment hydration with 2 liters of fluid prior to a cisplatin infusion is recommended and should adhere to institutional standards.
-

Adequate hydration and urinary output must be maintained during the following 24 hours. Other pretreatments such as anti-emetic prophylaxis and post-treatments such as hydration are up to the discretion of the Investigator.

OR

- Carboplatin, at AUC 5 IV bolus over 30 to 60 minutes, every 3 weeks for a maximum of 6 cycles. The carboplatin dose will be calculated using the Calvert formula:
  - AUC 5 is the target
  - Carboplatin Dose (mg) = 5 x ([glomerular filtration rate] GFR + 25)
  - Estimated serum creatinine clearance (mL/min) calculated using the modified Cockcroft-Gault equation ([Appendix 17.1](#)) can also be used as an estimate for GFR
  - The carboplatin dose is required to be re-calculated for every dosing based on the current GFR (or creatinine clearance as an estimate of GFR as per the protocol)
  - Pre- and post-treatments are up to the discretion of the investigator

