#### 3.1.2.1. Treatment Administration

[Figure 3.2](#) illustrates the order and timing of the treatments involved.

- Patritumab initial loading dose is 18 mg/kg IV (or placebo) over 60 minutes ( $\pm 10$  minutes) followed in cycle 2 and beyond with a maintenance dose of 9 mg/kg IV over 60 minutes ( $\pm 10$  minutes) every three weeks
  - Infusion time can be extended to a maximum of 120 minutes for subjects unable to tolerate the 60 minute infusion
- Cetuximab initial dose at 400 mg/m^2 IV as a 2-hour infusion followed by 250 mg/m^2 over 60 minutes weekly

One hour after the end of the cetuximab administration (on the weeks when cetuximab and platinum therapy are coadministered) infuse with either:

- Cisplatin at 100 mg/m^2 IV infused over 1 hour, every three weeks up to a maximum of 6 cycles
  - Pretreatment hydration with 2 liters of fluid prior to a cisplatin infusion is recommended and should adhere to institutional standards. Adequate hydration and urinary output must be maintained during the following 24 hours. Other pretreatments such as anti-emetic prophylaxis and post-treatments such as hydration are up to the discretion of the Investigator
  - This can be given in a separate infusion during patritumab and cetuximab infusion

[figure not shown]
OR

- Carboplatin, IV bolus over 30-60 minutes, every 3 weeks for a maximum of 6 cycles. The carboplatin dose will be calculated using the Calvert formula:
  - AUC 5 is the target
  - Carboplatin Dose (mg) = 5 x (glomerular filtration rate [GFR] + 25)
  - Estimated serum creatinine clearance (mL/min) calculated using the modified Cockcroft-Gault equation ([Appendix 17.1](#)) can also be used as an estimate for GFR

- The carboplatin dose is required to be re-calculated for every dosing based on the current GFR (or creatinine clearance as an estimate of GFR as per the protocol).
- Pre- and post-treatments are up to the discretion of the investigator

Note: It is important to use the infusion times given above for cisplatin and carboplatin; however, different infusion durations may be used if local practice dictates otherwise, except during Cycle 1, Day 1 for those subjects participating in the Intense PK sampling.

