#### Study Treatment

Information for dosing and administration is found in Section 3.1.2 . Study drugs should be administered consecutively in the order below:

- Administer patritumab IV as specified in Section 3.1.2
- Administer cetuximab IV as specified in Section 3.1.2
- Administer cisplatin (or carboplatin) IV one hour after cetuximab, as specified in Section 3.1.2.

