p Cisplatin infusions administered at 100 mg/m^2 IV over 1 hour and every 3 weeks up to a maximum of 6 cycles. For pre- and post-treatment hydration see [Section 3.1.2.1](#) and according to institutional standards. Creatinine clearance required prior to cisplatin administration. Cisplatin administered 1 hour after cetuximab administration. If carboplatin is selected instead of cisplatin, administer carboplatin at AUC of 5 over 30-60 minutes every 3 weeks for a maximum of 6 cycles. See [Section 3.1.2.1](#) for carboplatin.

q Genetic sampling is optional.

- r Tumor measurements will be assessed per RECIST Version 1.1. Baseline scans to be performed as part of eligibility during Screening. Existing radiographic scans can be used for the baseline evaluation if the scans were performed within 4 weeks prior to randomization.
  - s Tumor assessments are to be performed every 6 weeks to Week 24 (+/- 3 days), then every 12 weeks (+/- 7 days) thereafter.
  - t After discontinuation from study treatment, follow-up information for survival will be obtained per telephone approximately every 3 months for a minimum of 13 months.
  - u Additional biomarker samples:
    - Collect blood sample for cfDNA predose Cycle 1 Day 1, predose Cycle 2 Day 1, End of Cycle 6, predose every 4 Cycles, at progression (end of study treatment), and 40 days after last dose of study drug administered.
    - Collect blood samples for exosome at: predose Cycle 1 Day 1, predose Cycle 2 Day 1, and End of Cycle 6. Refer to the laboratory manual for instructions on collection and management of samples.
- \* Can be collected on Days 8 and 15 in all subsequent cycles at the discretion of the Investigator.
- † Corresponds to Cycle 1, Day 21 (504 hrs)—see [Table 8.2](#).

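### The protocol does not give one clear starting carboplatin dose for subjects with baseline clearance of 30–59 mL/min

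*Protocol*

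**What the plan says.** **Who is concerned.** Inclusion criterion 8 (protocol Section 4.1.1) asks for a clearance or GFR of at least 60 mL/min for cisplatin and at least 30 mL/min for carboplatin. Subjects at 30–59 mL/min are therefore eligible on carboplatin only.

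**Where AUC 5 is given.**
- Section 3.1.2.1 sets a target AUC of 5 and the formula "Carboplatin Dose (mg) = 5 x (glomerular filtration rate [GFR] + 25" (closing bracket omitted here). It adds: "The carboplatin dose is required to be re-calculated for every dosing based on the current GFR".
- The synopsis says "Carboplatin, at AUC 5 IV bolus over 30 to 60 minutes".
- Footnote p of Table 17.2 says "administer carboplatin at AUC of 5 over 30-60 minutes every 3 weeks".
- Footnote a of Table 5.6 gives AUC 5 by Calvert as the initial dose.

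None of these has a renal exception. The synopsis, Section 3.1.2.1 and footnote p do not point to Table 5.6. The Cycle 1 Day 1 visit text (Section 6.2.1) sends the site to the general dosing section: "Administer cisplatin (or carboplatin) IV one hour after cetuximab, as specified in Section 3.1.2".

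**Where a lower dose is given.** The nephrotoxicity rows of Table 5.6 (Section 5.1.7.4) are keyed to "Baseline creatinine clearance", and their dose column is headed "Recommended Dose on Day 1". The entry for 41–59 mL/min begins "AUC 3.75 (25% dose reduction"; the entry for 30–40 mL/min is AUC 3.0, labelled a 40% reduction.

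The text of Section 5.1.7.4 also requires carboplatin to be reduced or stopped when renal function is moderately to severely altered. It gives no clearance bands and does not mention the starting dose.

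**The concern.** A site preparing the first infusion for a subject with a baseline clearance of, say, 35 mL/min finds AUC 5 in the dosing section and AUC 3.0 in a row that appears to describe exactly that subject. Two sites could start similar subjects at different platinum doses and each cite the protocol.

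An error in either direction matters. Section 5.1.7.4 warns that people with abnormal kidney function are prone to serious and long-lasting marrow suppression on carboplatin. An unintended cut, on the other hand, under-doses the background therapy. Section 6.4 allows no deviations and asks sites to report dosing deviations to the sponsor, yet a monitor could not say which of the two first doses is the deviation.

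**Working it through.** **Inputs.** The Calvert form and AUC 5 come from Section 3.1.2.1. AUC 3.75 (41–59 mL/min) and AUC 3.0 (30–40 mL/min) come from Table 5.6. The clearance limits come from inclusion criterion 8.

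**Step 1: reproduce the table's own percentages.** 1 − 3.75/5 = 25% and 1 − 3.0/5 = 40%. Both are correct, and both use AUC 5 as the reference.

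**Step 2: dose under each reading.** Dose (mg) = AUC × (clearance + 25).

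| Clearance (mL/min) | AUC 5 | Table 5.6 | Gap (mg) | Ratio |
|---|---|---|---|---|
| 30 | 5 × 55 = 275 | 3.0 × 55 = 165 | 110 | 1.67 |
| 35 | 5 × 60 = 300 | 3.0 × 60 = 180 | 120 | 1.67 |
| 40 | 5 × 65 = 325 | 3.0 × 65 = 195 | 130 | 1.67 |
| 41 | 5 × 66 = 330 | 3.75 × 66 = 247.5 | 82.5 | 1.33 |
| 50 | 5 × 75 = 375 | 3.75 × 75 = 281.25 | 93.75 | 1.33 |
| 59 | 5 × 84 = 420 | 3.75 × 84 = 315 | 105 | 1.33 |

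**Step 3: what Calvert already does.** At clearance 60 the dose is 5 × 85 = 425 mg. At clearance 30 it is 275 mg, which is 1 − 275/425 = 35% lower without any change of AUC. Adding the table's cut gives 165 mg, which is 1 − 165/425 = 61% below 425 mg. The open question is whether the table's cut applies on top of Calvert at the first dose.

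**Step 4: which reading the text favours.**
- *For on-treatment use:* Section 5.1.7 opens by limiting itself to people already on treatment. The table's title refers to toxicities. The asterisk on the nephrotoxicity row stops carboplatin if events have not recovered within 3 weeks. Footnote a gives AUC 5 as the initial dose, and Section 6.2.1 leads to AUC 5.
- *For a starting-dose rule:* the rows are keyed to baseline clearance, which is not an on-treatment value. Section 3.1.2.1 calls for the current GFR at each dose, so a rule for later cycles would not naturally be keyed to baseline.
- *Neutral:* Day 1 does not identify Cycle 1. Every cycle has a Day 1 on which platinum may be given (Sections 6.2.6 and 6.2.7), and GFR is estimated before each platinum dose (Section 9.7).

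**Step 5: effect on the exposure summary.** SAP Section 8.3.6 defines dose intensity as 3 × cumulative dose / duration in weeks, and takes 5 × (creatinine clearance + 25) as the planned dose. Over n on-schedule cycles the duration is 3n weeks, so dose intensity equals the dose per cycle. With stable clearance, a subject dosed at the table's AUC in every cycle would show 3.75/5 = 75% or 3.0/5 = 60% relative dose intensity despite full compliance.

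**The case against.** The strongest reply is that the protocol, read as a whole, already answers the question. AUC 5 appears in every dosing instruction, the Day 1 visit text points there, and Table 5.6 belongs to a section on managing toxicity in people already being treated. Footnote a is then no contradiction: it hangs on the dose-reduction heading and supplies the reference for the 25% and 40%. The dose column speaks only of a recommended dose. Section 5.1.7 invites questions on dose changes to the medical monitor, and both that section and the table note refer to product information, so two sites diverging unnoticed is less likely.

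Much of this stands. It makes AUC 5 the better-supported starting dose, and it rules out two stronger conclusions that a reader might draw. One is that Table 5.6 plainly sets a reduced first dose; the scope of Section 5.1.7 and footnote a speak against that. The other is that the Day 1 heading means Cycle 1 Day 1; in this protocol it need not.

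The reply does not explain the word baseline. If the rows are for renal decline on treatment, that heading is wrong. If the heading is right, the dosing sections lack an exception. Asking the medical monitor resolves single cases, not the text, and the package insert is not among the documents.

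**Conclusion.** The protocol leaves the starting carboplatin dose unclear for subjects with a baseline clearance of 30–59 mL/min. The weight of the text favours AUC 5 with the table rows as on-treatment rules, but one heading contradicts this and nothing states an order of precedence. The first doses at stake differ by 82.5–105 mg (1.33-fold) at 41–59 mL/min and by 110–130 mg (1.67-fold) at 30–40 mL/min.

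These sizes rest only on the protocol's formula and printed AUC values. The number of subjects affected cannot be derived from the documents, nor can the dose that the sponsor intended.

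A reader might infer that the efficacy comparison is at risk. The documents do not support that: carboplatin is background therapy in both arms, and neither the sample size nor the primary PFS test depends on this rule. The issue is safety and consistent dosing, and it should be corrected because the subjects concerned are those the protocol singles out for severe marrow toxicity.

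**What to change.** Make the text give one rule. The sponsor should say which was intended.

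**Change that agrees with most of the documents.** Keep AUC 5 by Calvert as the Cycle 1 dose, and re-head the Table 5.6 nephrotoxicity rows as on-treatment rules, for example *Creatinine clearance before the current cycle* and *Dose for that cycle*. Cost: two table headings; no change to the Section 8.3.6 planned dose.

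**If a reduced starting dose was intended.** State AUC 3.75 (41–59 mL/min) and AUC 3.0 (30–40 mL/min) as explicit exceptions in Section 3.1.2.1, the synopsis, footnote p of Table 17.2 and footnote a of Table 5.6. Make matching edits in the SAP: Section 3.1, footnote p of Table 3.1.1, and the planned carboplatin dose in Section 8.3.6. Without the last edit, fully compliant subjects would be reported at about 75% or 60% relative dose intensity. Cost: four protocol places and three SAP places.

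Neither route changes the sample size, the visit schedule or any efficacy analysis.

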### 5.1.8. Retention Samples

Not Applicable.

### 5.1.9. Emergency Unblinding

In the case of a rare emergency where, in the opinion of the Investigator, discontinuation of study drug is not sufficient and study treatment must be unblinded to evaluate a further course of medical treatment, the following procedures will apply:

The investigator is encouraged to contact the CRO medical monitor to discuss their rationale for unblinding. However, to prevent delays to the investigator or medical personnel responding to a potentially emergent situation, unblinding of the study treatment will not be dependent upon the investigator receiving approval from the CRO medical monitor (ie, the Investigator will be able to obtain the code break information independent of the CRO medical monitor).

The method for determining a subject's treatment assignment once a subject is randomized in the study is through the IxRS. The investigator and one designated sub-investigator will have access to perform emergency unblinding in the IxRS. The treatment assignment of the selected subject randomized at their site will be revealed to the investigator performing the IxRS call upon completion of the emergency unblinding call.

The investigator must contact CRO medical monitor by telephone with an explanation of the need for opening the treatment assignment code within 24 hours of opening the code.

In the event of emergency unblinding, the subject will be informed about their treatment assignment. Information about the treatment assignment must be restricted to designated study site staff/personnel who are providing immediate care to the subject. Any documentation of the treatment assignment must be maintained separately (ie, a secured

file). The information must not be included in the subject's source files to ensure the treatment assignment will remain blinded to the CRO monitor and other study personnel who are not involved with the subject's immediate care.

When an emergency unblinding has occurred, an automatic notification (via e-mail) will be sent to the investigator and selected Daiichi Sankyo study personnel from the IxRS vendor. The notification will not contain any unblinding information. This will trigger the follow up process to document the unblinding by completing the Emergency Unblinding by Investigator Form (to be provided to the CRO medical monitor by study personnel upon receipt of IxRS notification) and submission to Daiichi Sankyo Clinical Safety and Pharmacovigilance; please refer to the form for completion instructions.

Once the study treatment has been unblinded for a specific subject, the study treatment should be discontinued for the subject, and the subject should leave the study treatment phase. The end of treatment and follow-up assessments for the subjects will be performed as defined in the protocol.

